7.9 DATA ANALYSIS

All analysis will be performed with SAS Inc, Version 9.3.

7.9.1 MAIN ANALYSIS

All analyses will be conducted in both data sources and may be combined in pooled analyses if appropriate, based on homogeneity of treatment effect. Pooling of results across data sources will correspond to a weighted average effect (as in a fixed effects meta-analysis) using the Mantel-Haenszel method. [\[R97-0509\]](#) Heterogeneity will be assessed by comparing the treatment effect point estimates across data sources. If there is a difference >30% in the overall effect measure for a primary outcome across the two data sources, we will conduct an additional investigation that assesses treatment effect within levels of protocol-specified subgroups (Section 6.9.2) separately by a database. If treatment effect is different across levels of the subgroup variable within a data source, and the distribution of this subgroup variable differs by data source, then the pooling will be conducted within strata of the subgroup variable or variables across which heterogeneity is observed to account for this heterogeneity (see Section 6.2 for more details). In each data source, we will compare distributions of socio-demographic, clinical and utilization characteristics among initiators of different anticoagulant agents, and calculate event rates during follow-up for each of the specified outcomes.

Unadjusted and adjusted relative risks (hazard ratios) and rate differences will be estimated. In adjusted analyses, we will use propensity score (PS) matching to balance potential confounders. [\[R13-1120\]](#) [\[R12-1912\]](#) PS will be derived from predicted probabilities of treatment initiation, given all measured covariates. We will estimate the primary propensity score for each patient using a logistic regression model that includes all pre-defined covariates (from Section 6.4.3). The propensity score will be used to match dabigatran initiators to initiators of warfarin on a 1:1 fixed ratio basis using a nearest-neighbor algorithm and a caliper of 0.05. In addition, patients will be matched on calendar quarter of initiation. Individual covariates will be further tabulated and compared across matched cohorts. If substantial covariate imbalance between dabigatran and warfarin is noted as assessed by a standardized difference >0.1, then we will further adjust the outcome models for HAS-BLED and CHA₂DS₂-VASC score as Cohort Phase 1 results indicated that these scores include all the variables typically imbalanced.

We will plot post-PS-matching Kaplan-Meier curves for event-free survival as a function of the duration of use of the index anticoagulant agent to evaluate the proportionality of hazards.

The secondary analyses will involve other NOAC medications as compared to warfarin. Other NOACs will include rivaroxaban, apixaban and others once they become available for stroke prevention in NVAF patients. We will monitor the number of patients initiating other NOACs and provide these numbers along with power calculations for primary outcomes at each interim report. Once sufficient numbers have accrued, and sufficient follow up time is available, these other NOAC initiators will be separately matched to warfarin initiators and primary analyses (and further/sensitivity analyses if numbers allow) as described above for dabigatran-warfarin comparison will be done.

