7. RESEARCH METHODS

7.1 STUDY DESIGN

This study will involve a sequentially built parallel cohort design with propensity score (PS) matching to address potential confounding. Each new data update will provide additional follow-up time on the patients already in the cohort, as well as new initiators who will be matched on PS and calendar quarter of initiation and added to the existing cohort for the cumulative analyses. This study design was selected to facilitate the inclusion of additional subjects and follow-up time as data become available over the course of the study period. The study will be conducted within two US-based longitudinal healthcare claims databases (MarketScan and UnitedHealth Research Database, see also section 6.5 for more details). Cohort selection and all analyses will be performed separately within each database and a combined analysis that pools results from the two databases for the same time periods will be done if appropriate, based on an assessment of homogeneity of treatment effect. Pooling of results across data sources will correspond to a weighted average effect (as in a fixed effects meta-analysis) using the Mantel-Haenszel method. [\[R97-0509\]](#) It is expected that there will be little heterogeneity of treatment effects across the databases since the databases are similar with respect to who is included in the database (employed people and their dependents) and the nature of data captured (health insurance transactions billed on a negotiated fee for service basis). Heterogeneity will be assessed by comparing the treatment effect point estimates across data sources. Assessment of heterogeneity will not rely on a statistical test of heterogeneity, since the large study size may indicate significant heterogeneity ($p < 0.05$) even if estimates are similar (i.e. a difference that is not clinically meaningful) and the purpose of this assessment of heterogeneity is intended only for determining whether it is reasonable to combine data sources. If contrary to expectations, there is a difference $> 30\%$ in the overall effect measure for a primary outcome across the two data sources, we will conduct an additional investigation that assesses treatment effect within levels of protocol-specified subgroups (Section 6.9.2) separately by a database. If treatment effect is different across levels of the subgroup variable within a data source, and the distribution of this subgroup variable differs by data source, then the pooling will be conducted within strata of the subgroup variable or variables across which heterogeneity is observed to account for this heterogeneity.

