7.7 STUDY SIZE

The ability of this research program to detect a given risk increase depends on the incidence of the outcome as well as the number of cohort entrants and duration of follow-up. The study size will depend on the number of dabigatran (or other NOAC medications) and warfarin initiators who meet the study inclusion and exclusion criteria and are successfully matched into cohorts. On the basis of the outcome incidence rate observed in the comparison group in the pilot phase of this project (Phase 1) and the cumulative person-time of observation over the study period, we estimated the minimum relative rate that can be detected with 80% power for dabigatran-warfarin comparison.. During the period October 2010 – June 2012, among patients with a minimum of 12 months baseline history, no prior use of any anticoagulants, and a diagnosis of non-valvular atrial fibrillation, there are 4,158 dabigatran incident users in the UnitedHealth database and approximately 20,000 dabigatran users in MarketScan database. These dabigatran users will be matched to a similar number of warfarin incident users. Assuming that approximately 70% of patients will be matched, an average follow-up of 5 months (both based on the preliminary results from Phase 1 of the BI/ Pradaxa project) and the additional users who initiated dabigatran during July-December 2012 period, there should be slightly more 10,000 person-years of dabigatran follow-up for the initial analysis. As this project expands in 6 month increments, the person-time, along with outcomes and the ability to detect a particular relative risk will increase.

The table below provides estimates of the minimum relative rates that can be detected with 80% power for the major study outcomes under specific assumptions regarding their incidence in the comparator group (labeled “base rate”) and the accrual of person-time. The base case incidence rates are the rates observed in warfarin initiators who were calendar quarter- and PS- matched to dabigatran initiators during the October 2010-June 2012 period in the UnitedHealth database (Phase 1 of the project). We conservatively assumed that the number of patients initiating dabigatran each month during July 2012 – December 2015 is equal to the average monthly number of initiators during the first half of 2012, that at least 2/3 of these patients are matched 1:1 to comparator patients, and that each patient contributes 0.41 years of follow-up time.

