13. ANNEX

ANNEX 1: LIST OF STAND-ALONE DOCUMENTS

None

Table A3 Follow-up and outcomes among matched cohorts

Group	Size	Follow-up (P-Y)	Outcome events	Incidence Rate	HR	95% CI
Dabigatran	N					
Warfarin	N					

[figure not shown]
This table will be repeated for each of the outcomes

Table A4 Follow-up and distribution of reasons for discontinuation

Group	Size	Follow-up (years)			Reasons for discontinuation (N, %)					
		Mean	Median	Max	Discontinue	Switch	Event	Disenrollment	Death	Nursing home admission
Dabigatran	N									
Warfarin	N									

This table will be repeated for each of the outcomes.

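### Does naming Mantel-Haenszel for pooling, and leaving the 30% rule without a scale, make the combined hazard ratio ambiguous?

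*Combined protocol and SAP*

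**What the plan says.** Sections 7.1 and 7.9.1 describe pooling in the same terms: "Pooling of results across data sources will correspond to a weighted average effect (as in a fixed effects meta-analysis) using the Mantel-Haenszel method". Section 7.1 adds that cohort selection and all analyses are done separately in each database, and that the combined analysis pools the results if that is judged appropriate.

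On the effect measure, section 7.9.1 says "Unadjusted and adjusted relative risks (hazard ratios) and rate differences will be estimated". Shell Table A3 ("Follow-up and outcomes among matched cohorts") has columns for events, person-years, incidence rate, HR and 95% CI. If covariates remain unbalanced after matching, "assessed by a standardized difference >0.1, then we will further adjust the outcome models for HAS-BLED" and CHA₂DS₂-VASc.

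Heterogeneity between the databases is judged on point estimates. Section 7.1 explains why: "Assessment of heterogeneity will not rely on a statistical test of heterogeneity, since the large study size may indicate significant heterogeneity". The rule in 7.9.1 begins "If there is a difference >30% in the overall effect measure for a primary outcome across the two data sources" and leads to an investigation within subgroups. Pooling then becomes stratified only if the effect varies across a subgroup within a database and that subgroup is also distributed differently in the two databases.

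**The concern.** Mantel-Haenszel applied to events and person-time estimates a rate ratio. A fixed-effect meta-analysis of hazard ratios averages log hazard ratios. The pooling sentence names the first and likens it to the second, without stating inputs or weights, so two programmers could build different estimators from it.

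The difference could matter when the imbalance rule fires. The database-specific hazard ratios would then be adjusted for the two scores, while a Mantel-Haenszel figure built from counts with database as the only stratum would not. The pooled figure would no longer be an average of the hazard ratios printed beside it, and could retain confounding already removed from them.

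The 30% rule has a similar gap. Hazard ratios of 0.70 and 0.95 differ by 36% of the smaller (0.95/0.70 = 1.357), by 26% of the larger (1 − 0.70/0.95 = 0.263), and by 0.25 in absolute terms. Only the first reading crosses 30%, and the choice could be made after seeing results at any of seven reports.

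**Working it through.** **Inputs.** Person-years per group are 10,000 at Interim report 1 and 24,100 at the final report (abstract, expected study size; Table 8). Base rates are 31.59 per 1,000 person-years for stroke and 66.72 for major hemorrhage (Table 8). For the database split, section 7.7 says "there are 4,158 dabigatran incident users in the UnitedHealth database and approximately 20,000 dabigatran users in MarketScan database", so the UnitedHealth share is 4,158/24,158 = 17.2%. Section 7.7 also assumes that "each patient contributes 0.41 years of follow-up time". My assumptions: both databases have the same base rate, the matched split equals the initiator split, and the true hazard ratio is the same in both.

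**Table 8 first.** With events d = rate × person-years × (1 + RR) and power = Φ(ln RR × √(d/4) − 1.96), solving for 80% power gives:

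| Outcome | Interim 1, computed (stated) | Final, computed (stated) |
|---|---|---|
| Stroke | 1.235 (1.24) | 1.149 (1.15) |
| Major hemorrhage | 1.159 (1.16) | 1.101 (1.10) |

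The event counts used below therefore match the plan's.

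**The two estimators without a triggered adjustment.** For database i, let aᵢ and bᵢ be dabigatran and warfarin events, T₁ᵢ and T₀ᵢ the person-times, and Tᵢ their sum.

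- Mantel-Haenszel: Σ(aᵢT₀ᵢ/Tᵢ) / Σ(bᵢT₁ᵢ/Tᵢ). With equal person-time per group this reduces to Σaᵢ/Σbᵢ.
- Inverse variance: exp[Σwᵢ ln(aᵢ/bᵢ) / Σwᵢ], with wᵢ = 1/(1/aᵢ + 1/bᵢ).

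Stroke at Interim report 1 has 31.59 × 10 = 315.9 expected events per group at hazard ratio 1: 54.4 in UnitedHealth and 261.5 in MarketScan. Results of 400,000 Poisson draws, with the true hazard ratios assumed:

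| True HR | Mantel-Haenszel mean | Inverse-variance mean | 95th percentile of relative difference |
|---|---|---|---|
| 1.00 | 1.0001 | 1.0001 | 0.12% |
| 0.80 | 0.7997 | 0.8000 | 0.19% |
| 0.65 | 0.6495 | 0.6501 | 0.34% |

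The gaps are smaller for major hemorrhage and at the final report. For scale, the standard error of the pooled log ratio here is √(2/315.9) = 0.080 at hazard ratio 1 and √(1/315.9 + 1/(0.65 × 315.9)) = 0.090 at 0.65. If the databases truly differ, with 0.70 in UnitedHealth and 0.90 in MarketScan, expected counts give 0.8656 against 0.8661. The widest gap in the cases tried was 0.8484 against 0.8500 (0.60 and 0.90).

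**The 30% rule.** The standard error of the log ratio of the two hazard ratios is √(2/e_U + 2/e_M), where e is expected events per group. Stroke at Interim report 1: √(2/54.4 + 2/261.5) = 0.211. The chance of a ratio above 1.3 or below 1/1.3 with no true difference is 2 × [1 − Φ(0.262/0.211)] = 21%.

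| Outcome, report | SE | Chance beyond 1.3 either way | Ratio needed for p<0.05 |
|---|---|---|---|
| Stroke, Interim 1 | 0.211 | 21% | 1.51 |
| Stroke, Interim 6 | 0.143 | 6.6% | 1.32 |
| Stroke, final | 0.136 | 5.3% | 1.305 |
| Major hemorrhage, Interim 1 | 0.145 | 7% | 1.33 |
| Major hemorrhage, Interim 2 | 0.131 | 4.4% | 1.29 |
| Major hemorrhage, final | 0.093 | 0.5% | 1.20 |

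Other readings of 30% at hazard ratio 1 give 9% to 16% for stroke at Interim report 1 and about 1% to 3% at the final report. These are rates of starting an extra investigation, not of reaching a wrong conclusion.

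**The case for a change.** The best case for a change rests on the imbalance trigger. Section 7.9.1 itself refers to variables that tended to stay unbalanced in Phase 1, so the trigger is plausible. One can build an example with a score imbalance of −0.12 standard deviations, a rate ratio of 1.4 per score point and a true hazard ratio of 0.80. Mantel-Haenszel by database alone then gives 0.754, against 0.80 for averaged adjusted estimates. The mechanism is real, but neither the imbalance nor the gradient appears in the documents, so the example does not size anything for this study. It also needs a reading in which the pooled results are raw counts. Stratifying Mantel-Haenszel by score level as well recovers 0.80 in the same example, so the method is not inherently unable to carry the adjustment.

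A second argument is that the stated reason for avoiding a heterogeneity test does not fit stroke, where p<0.05 would need a ratio above 1.3 at every interim report. On the base inputs that is so, but narrowly by Interim report 6 (1.32): a UnitedHealth share of 21% instead of 17.2% brings it to 1.296. For major hemorrhage the reason holds from Interim report 2 onward.

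The obvious replacement has its own cost. Inverse-variance pooling of log hazard ratios fails when a group has no events. Hemorrhagic stroke at Interim report 1 has about 2.09 × 10 × 0.172 = 3.6 expected UnitedHealth events per group. The chance that at least one group is empty is 1 − (1 − e^−3.6)² ≈ 5% at hazard ratio 1, and about 19% at an assumed 0.5. Mantel-Haenszel copes with that.

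What stands is that the weights for the hazard ratio and the scale of 30% are not written down in 7.1 or 7.9.1. The subgroup section that both cross-reference as 6.9.2 is not in the text available here and may say more.

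**Conclusion.** No change to the plan is called for. The pooling sentence labels its method loosely, but separate analysis by database followed by a weighted average of effects leads an analyst to combine the two hazard ratios from the outcome models actually fitted, adjusted where the imbalance rule has fired. Naming Mantel-Haenszel is not itself an error, since rate differences are also planned and it suits them.

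For the primary outcomes without a triggered adjustment, the alternative reading moves the pooled estimate by at most 0.34% in 95% of simulated analyses. That rests on constant hazards, equal person-time per group and equal base rates in the two databases. The documents do not allow the effect to be sized under non-constant hazards with unequal persistence, or under a triggered adjustment on the count-based reading.

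The open scale of the 30% rule changes how often an additional investigation starts, from roughly 9% to 21% of stroke analyses at Interim report 1 at a true hazard ratio of 1. It does not by itself alter the pooled estimate: two further conditions must hold before pooling becomes stratified. The database-specific hazard ratios and intervals let a reader compute their ratio and judge it directly. This is missing detail that competent analysts fill sensibly, with no shown gain from amending the text.

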7.4 VARIABLES

7.4.1 EXPOSURES

Table 1 Market availability for the treatments of interest

Class	Drug	FDA approved*	FDA approved for stroke prevention in patients with non-valvular atrial fibrillation at risk for stroke
Direct thrombin inhibitors	Dabigatran	19 October 2010	19 October 2010
Direct Xa inhibitors	Rivaroxaban	1 July 2011	4 November 2011
	Apixaban	28 December 2012	28 December 2012

Table 1 (con't)

Market availability for the treatments of interest

Edoxaban	Phase III	N/A
Otamixaban	Phase III	N/A
Betrixaban	Phase II	N/A

*as of December2013

The primary contrast of interest is between new initiators of warfarin and new initiators of dabigatran, defined as no anticoagulation with *any oral anticoagulant* in the 12 months before the index prescription.

In the secondary analysis and as they become available for stroke prevention in NVAF patients, other NOAC medications will be compared to warfarin. The same definitions and inclusion/exclusion criteria will be applied.

Concomitant therapy with medications that are not cohort-defining medications (defined as simultaneous use on the day of dabigatran or warfarin initiation) will be accounted for in the study analyses as a covariate and used for balancing or stratification.

Study follow-up

We will follow patients for each of the outcomes of interest in a prospective manner and we will estimate measures of effect using person-time based analyses.

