The primary analyses will use an 'as treated' approach. Follow-up will start the day after cohort inclusion, which is the day of treatment initiation, and will end at the time of disenrollment, end of the observation period (available data), death, admission to a nursing home, discontinuation of the index study exposure, or switch to a different anticoagulant whichever comes first. Exposure will be considered discontinued if there is a treatment gap ≥ 14 days from the end of calculated days supplied. Warfarin therapy involves dose titration following initiation before a stable therapeutic INR is obtained. We will use the reported days' supply as a proxy for duration of exposure following a dispensing as it may more adequately reflect the use pattern within a commercial health insurer database represented by UnitedHealth and MarketScan. This approach involves a potential mismatch between the presumed exposure derived from dispensing data and actual exposure. The utilization study (described in study protocol 1160.177) will inform the sensitivity analyses around this assumption and seek to clarify how sensitive results are to variations in the exposure assumption. Switchers will be censored in the as-treated approach on the day of the dispensing of the alternative medication. If switching was the consequence of a side effect of a drug, most likely the index drug was discontinued for some time before the new drug was initiated. Any clinical event therefore was most likely recorded during that period and will be

attributed to the index drug.

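### Crude as-treated rate differences can mix a drug effect with unequal persistence if the event hazard changes after initiation; add risk differences at fixed times.

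*Combined protocol and SAP*

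**What the plan says.** The main analysis (7.9.1) will "calculate event rates during follow-up for each of the specified outcomes" and then states that "Unadjusted and adjusted relative risks (hazard ratios) and rate differences will be estimated". It gives no formula for the rate difference. Under study follow-up, section 7.4.1 adds that "we will estimate measures of effect using person-time based analyses".

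Follow-up is tied to treatment: "The primary analyses will use an 'as treated' approach". It ends, among other reasons, at a switch or at discontinuation, defined thus: "Exposure will be considered discontinued if there is a treatment gap ≥ 14 days from the end of calculated days supplied". The same rule applies to both arms, but each patient's own dispensing record decides when it takes effect.

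Shell Table A3, "Follow-up and outcomes among matched cohorts", carries the columns "Follow-up (P-Y) Outcome events Incidence Rate" followed by a hazard ratio and confidence interval. It has one row per arm, no split by time since initiation and no rate-difference column. Table A4, "Follow-up and distribution of reasons for discontinuation", shows mean, median and maximum follow-up by arm. Section 7.9.1 also plans Kaplan-Meier curves in the matched cohorts by duration of use; their stated purpose is to check proportional hazards.

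**The concern.** A crude rate is the average hazard over the person-time that an arm happens to supply. Matching on propensity score and calendar quarter balances patients at initiation, not how long they stay on treatment. If one arm stops sooner, more of its person-time lies in the early period. If the hazard is then higher or lower than later, that arm's crude rate moves for a reason unrelated to the drug.

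A hazard ratio that compares patients at the same time since initiation does not have this problem, provided stopping is unrelated to risk. One report could therefore show a hazard ratio of 1 beside a non-zero rate difference. The proportional-hazards check would not reveal this, because the artefact arises even when hazards are exactly proportional. At stake is the rate difference, the only absolute effect measure that 7.9.1 names.

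**Working it through.** **Inputs from the documents**
- Base rates in matched warfarin initiators (Table 8): major hemorrhage 66.72 and stroke 31.59 per 1,000 person-years (PY).
- Person-time per arm: 10,000 PY at interim report 1 and 24,100 PY at the final report.
- Mean follow-up: about 5 months, or 0.41 years (7.7), one figure for both arms.

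**The plan's own figure.** Table 8 is reproduced for both primary outcomes by solving ln(RR) = (1.960 + 0.842) × √(1/E + 1/(E·RR)), where E is base rate × PY per arm. For major hemorrhage at the final report, E = 0.06672 × 24,100 = 1,608 and RR = 1.101 (stated 1.10). For stroke at interim report 1, E = 315.9 and RR = 1.236 (stated 1.24). A ratio of 1.10 on 66.72 is a difference of about 6.7 per 1,000 PY.

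**Assumptions, none of them in the documents.** Time on treatment is exponential with mean m months. Both arms share one hazard: h1 in the first 3 months and h2 afterwards, with h1 = k·h2. It is scaled so that the crude rate equals the base rate at m = 5. Depletion by events is ignored, which is negligible at these rates.

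**Formula.** The share of person-time in the first 3 months is s(m) = 1 − exp(−3/m). The crude rate is h1·s + h2·(1 − s) = h2·[1 + (k − 1)·s]. The false rate difference is therefore (k − 1)·h2·[difference in s].

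- **Constant hazard, k = 1:** the difference is exactly 0, however unequal the stopping.
- **Shares:** s(4) = 0.5276, s(4.5) = 0.4866, s(5) = 0.4512, s(5.5) = 0.4204, s(6) = 0.3935.
- **k = 2:** h2 = 66.72 / 1.4512 = 45.98 and h1 = 91.95. At m = 4 the rate is 45.98 × 1.5276 = 70.2. At m = 6 it is 45.98 × 1.3935 = 64.1. The difference is 6.2 and the rate ratio 0.91.
- **Other multiples:** h2 = 66.72 / 1.2256 = 54.44 for k = 1.5, and 66.72 / 1.9024 = 35.07 for k = 3.

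False difference for major hemorrhage, per 1,000 PY:

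| Means (months) | k = 1.5 | k = 2 | k = 3 |
|---|---|---|---|
| 4.5 vs 5.5 | 1.8 | 3.0 | 4.6 |
| 4 vs 6 | 3.7 | 6.2 | 9.4 |

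For stroke, multiply by 31.59 / 66.72 = 0.473. At 4 vs 6 months this gives 1.7, 2.9 and 4.5.

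**Sampling noise.** The SE of a rate difference is 1000 × √(2 × rate / PY). At the final report it is 1000 × √(2 × 0.06672 / 24,100) = 2.35 for major hemorrhage and 1.62 for stroke, so 1.96 × SE is 4.6 and 3.2. At interim report 1 the corresponding limits are 7.2 and 4.9.

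**Does a fixed-time risk difference remove it?** With k = 2, the cumulative hazard at 3, 6 and 12 months is 0.0230, 0.0345 and 0.0575. The risks are 2.3%, 3.4% and 5.6%. They depend only on the hazard, so they are the same in both arms and the risk difference is 0 whatever the stopping speeds.

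**The case against.** The strongest reply is that the artefact needs two conditions and the documents establish neither. Sample sizing uses one mean follow-up and equal person-years per arm, and no hazard by time since initiation is given. A reader might infer that unequal stopping alone makes two equivalent drugs look different. It does not: with a constant hazard, and stopping unrelated to risk, the rate difference is zero.

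A reader might also take the remark on warfarin dose titration in 7.4.1 as evidence of a high early hazard. That remark introduces the choice of days' supply as a proxy for exposure and says nothing about event risk. It also concerns warfarin only. An early excess in one arm would be non-proportional hazards, a different problem from the shared early hazard assumed here.

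Other parts of the objection also stand:
- Forming the rate difference from the Table A3 rates is an inference, although nothing in the text available points elsewhere.
- The Kaplan-Meier curves put absolute risk on a common time axis, and Table A4 would reveal unequal follow-up.
- 7.9.1 and 7.11 refer to subgroup and further-analysis sections that are not in the text available, so a remedy there cannot be ruled out.
- Several scenarios lie below sampling noise, especially at early interim reports and for stroke.

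What does not stand is that these safeguards settle the matter. The curves are planned only to check proportionality, and Table A4 displays unequal follow-up without correcting the rates for it.

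**Conclusion.** The point holds conditionally. If the hazard varies with time since initiation and persistence differs by arm, the planned crude rates compare different time windows, and the rate difference can depart from zero when the drugs have identical hazards. The available text specifies no common window or standardisation.

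The size is illustrative and rests on the assumed exponential stopping times, the 3-month change point and the early-hazard multiple. For major hemorrhage most scenarios give about 3 to 9 per 1,000 PY, with 1.8 in the mildest, against noise of 4.6 at the final report. For stroke, 4 vs 6 months with a 2-fold early hazard gives about 2.9 against 3.2. The artefact can thus be below or above sampling noise, and a hazard that rises with time would reverse its sign.

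The documents do not support the stronger reading that the rate differences will be biased, or that they must be dropped. This is a cheap improvement, not a flaw that undermines the study.

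**What to change.** In 7.9.1 and Table A3, add the risk difference with its confidence interval at fixed times since initiation, for example 90, 180 and 365 days, taken from the matched Kaplan-Meier curves already planned. State that conclusions about absolute effect rest on it. Keep the crude rates and rate difference as descriptive, to be read alongside follow-up by arm in Table A4.

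The cost is a few lines of SAP text and a few table rows, using data already held. Intervals will be somewhat wider, most of all at later times. Under exponential stopping with a 5-month mean, about exp(−12/5) = 9% of patients are still followed at 12 months, roughly 60,000 × 0.0907 = 5,400 per arm at the final report. Like the hazard ratio, the added measure assumes that stopping is unrelated to risk, so it does not address risk-related stopping.
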